6.2.1.3 Dose Escalation and Dose Reduction Decisions

If none of the initial dose evaluation group subjects experience a DLT, subjects in the treatment phase who have not yet received NTLA-5001 and subsequent subjects entering the treatment phase will be eligible for the next dose escalation cohort.

If 1 of the initial dose evaluation group subjects experiences a DLT, enrollment will continue in the dose evaluation group for 3 additional subjects. When the last subject in the expanded dose evaluation group has been observed through Day 28:

- If no subject in the expanded dose evaluation group experiences a DLT, subjects in the treatment phase who have not yet received NTLA-5001 and subsequent subjects entering the treatment phase will be eligible for the next dose escalation cohort.
- If 1 or more additional subject in the expanded dose evaluation group experiences a DLT, no dose escalation will be proposed. Subjects in the treatment phase who have not yet received NTLA-5001 and subsequent subjects entering the treatment phase will be eligible for Dose Level -1 if DLTs are seen at Dose Level 1, or the next lower dose level will be declared the maximum tolerated dose (MTD), if DLTs are seen at Dose Level 2 or 3. Fewer than 2/6 subjects with DLTs will establish the MTD.

If 2 or 3 of the initial dose evaluation group experiences a DLT, no dose escalation will be proposed. Subjects in the treatment phase who have not yet received NTLA-5001 and subsequent subjects entering the treatment phase will be eligible for Dose Level -1 if DLTs are seen at Dose Level 1, or the next lower dose level will be expanded to 6 subjects if DLTs are seen at Dose Level 2 or 3. Fewer than 2/6 subjects with DLTs will establish the MTD.

If a dose escalation is proposed, the subsequent cohort dose may be reduced or increased by up to 50% if the Sponsor and investigator agree, based on observations in the prior cohort. At the Sponsor's discretion, up to 6 subjects may be enrolled in any dose cohort for Arm 1 or Arm 2.

If a subject receiving out-of-specification cells has a DLT, this finding would not be attributed to DLT tally for a specific Dose Level; but would be reviewed as part of the overall safety profile in conjunction with planned safety reviews and by the Sponsor, investigators, and DMC. The event would be considered when making dose escalation decisions, stopping rule decisions, and/or dose selection for expansion cohort.

6.2.1.4 Simultaneous Escalation of Arm 1 and Arm 2

The risk of severe or serious adverse events after cell therapy is correlated with a subject's tumor burden ([Garcia-Manero et al, 2015](#); [Garzon et al, 2017](#)). Therefore, DLT information from Arm 2 subjects with $\geq 5\%$ bone marrow blasts may inform dose escalation decisions for Arm 1 subjects with $< 5\%$ bone marrow blasts. Simultaneous escalation of Arm 1 and Arm 2 may occur when the following criteria are met:

1. Dose escalation in Arm 2 is recommended from the current dose based on Dose Escalation and Dose Reduction criteria above; and
2. No subjects have experienced DLT at the current dose in Arm 1.

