4 STUDY DESIGN AND DOSE RATIONALE

4.1 Overall Study Design

This is Phase 1/2a, first-in-human, single-dose study to investigate NTLA-5001 in subjects with AML. The design is according to guidance for first-in-human trials and for the investigation of advanced therapy medicinal products, including the European Medicine Agency “Guideline on strategies to identify and mitigate risks for first-in-human and early clinical trials with investigational medicinal products”; and draft guidance “Guideline on quality, non-clinical and clinical requirements for investigational advanced therapy medicinal products in clinical trials”; and the FDA draft guidance “Acute Myeloid Leukemia: Developing Drugs and Biological Products for Treatment”. The design is to ensure the safety and well-being of trial subjects and to mitigate risk to the greatest extent possible.

This study consists of 2 phases: dose escalation and dose expansion. The dose escalation phase of the study will consist of up to 3 cohorts of subjects in Arm 1 and 3 cohorts of subjects in Arm 2. Each Arm 1 cohort will include up to 6 subjects, as detailed in dose escalation below. Each Arm 2 cohort will include 3 to 6 subjects. Once a dose is identified for detailed assessment of safety in Arm 1 subjects and 6 subjects have been enrolled at that dose, an expansion cohort will be opened for an additional 9 subjects in Arm 1. Once a dose is identified for detailed assessment of safety in Arm 2 subjects, a safety expansion cohort will be opened for an additional 9 subjects in Arm 2.

The screening period will be up to 28 days, and a subject that meets all inclusion and none of the exclusion criteria will be enrolled into the leukapheresis phase in Arm 1 for subjects with AML blasts <5% of bone marrow or in Arm 2 for subjects with AML blasts \geq 5% of bone marrow. During screening, MRD will be measured in bone marrow by central laboratory assessment. After study entry, subjects may have repeat BM assessment prior to Arm assignment based on whether screening biopsy was prior to study consent, interval since screening study, change in condition, or bridging therapy. If an Arm 1 subject is found to have \geq 5% bone marrow blasts at repeat BM assessment, the subject may be re-assigned to Arm 2 or, if Arm 2 is not yet enrolling subjects, the subject may receive NTLA-5001 at Dose Level -1.

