6.2 Dose Modification

6.2.1 Dose-Cohort Study Escalation, Dose Reduction, and Stopping Rules

6.2.1.1 Dose Escalation Scheme

Proposed Dose Escalation Cohort Number	Planned Dose
Dose Level -1	[REDACTED]
Dose Level 1	[REDACTED]
Dose Level 2	[REDACTED]
Dose Level 3	[REDACTED]

Subjects who enter the treatment group in Arm 1 or in Arm 2 will be assigned to the dose level cohort currently open for enrollment for the relevant Arm. Arm 1 and Arm 2 will be enrolled in parallel.

Up to 3 subjects will be enrolled in an initial dose evaluation group and will be treated with NTLA-5001 for Arm 1 and for Arm 2. Enrollment will be staggered as follows (see figure in Section 13.8):

- Staggering of enrollment across the 2 study Arms: Arm 1 and Arm 2 will be escalated independently. If an Arm 1 subject is dosed at a new dose level before an Arm 2 subject, the Arm 1 subject will be observed through Day 28 before dosing a subject in Arm 2.
- Staggering of enrollment within a dose level cohort (either Arm 1 or Arm 2): each of the first 3 subjects will be observed for 28 days before enrolling the next subject.
- Staggering of enrollment between Dose Levels: all subjects in a dose evaluation group will be observed for 28 days before any subject is enrolled at the next Dose Level.

Once the entire dose evaluation group for a study Arm has been observed for 28 days, all data, including DLT information from all cohorts in both Arms, will be reviewed by the Sponsor and treating investigators to consider dose escalation. The following study personnel must participate in review of the study data and dose escalation decision: the Intellia Medical Lead, the Intellia Safety Lead, and any Investigator who has treated a subject in the cohort that has just completed 28-day observation.

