9 STATISTICAL CONSIDERATIONS

9.1 Statistical Hypothesis

No hypothesis testing is to be performed in this first-in-human study.

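### After 0/3 DLTs the escalation condition reads only the first three subjects and Arm 1 expansion counts six enrolled, so 2/6 or 3/6 reached through subjects 4–6 meets no general written limit

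*Protocol*

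**What the plan says.** Protocol 6.2.1.1 sets the size of the first group: "Up to 3 subjects will be enrolled in an initial dose evaluation group". Protocol 6.2.1.3, repeated in the Synopsis, then has three branches.

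- **0 DLTs in the initial group.** The branch begins "If none of the initial dose evaluation group subjects experience a DLT, subjects in the treatment phase who have not yet received NTLA-5001" and makes these and later subjects eligible for the next level.
- **1 DLT.** "If 1 of the initial dose evaluation group subjects experiences a DLT, enrollment will continue in the dose evaluation group for 3 additional subjects". After that, "If 1 or more additional subject in the expanded dose evaluation group experiences a DLT, no dose escalation will be proposed".
- **2 or 3 DLTs.** There is no escalation. If this happens at Dose Level 2 or 3, the next lower level is filled to six.

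The sentence "Fewer than 2/6 subjects with DLTs will establish the MTD" closes the text of the stop outcome after 1/3 and of the 2–3/3 branch. It does not appear in the 0/3 branch.

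Two provisions put subjects 4–6 on a level that was 0/3. Section 6.2.1.3 says that, if the Sponsor chooses, "up to 6 subjects may be enrolled in any dose cohort for Arm 1 or Arm 2". Section 4.1, the Synopsis and SAP 2.2 open Arm 1 expansion as follows: "Once a dose is identified for detailed assessment of safety in Arm 1 subjects and 6 subjects have been enrolled at that dose".

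**The concern.** The expanded group in 6.2.1.3 exists only after 1/3. Subjects 4–6 added after 0/3 belong neither to the initial group nor to that expanded group, so the branch that has already permitted escalation does not read their DLTs. The same count at the same dose is then treated differently according to the order of events: one DLT in each set of three stops escalation, while none in the first three and two in the next three meets no stated stop.

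The Arm 1 trigger has a related weakness. Sections 4.1 and 8.1.1 use enrollment for a step before leukapheresis, and 6.2.1.1 assigns the dose level on entry to the treatment group, before infusion. Six enrolled can therefore be reached before subjects 4–6 finish the 28-day DLT window. Read literally, the six-subject requirement adds exposure without adding a stated toxicity check before nine more subjects are treated.

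**Working it through.** **Plan figures.** The documents give no operating characteristics for the escalation rule, and "No hypothesis testing is to be performed in this first-in-human study", so there is no power figure to reproduce. The planned numbers do reproduce: 2 arms × 3 cohorts × 6 = 36 in escalation, 2 × 9 = 18 in expansion, total 54.

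**Order of events at one level:**

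| First three | Next three | Total | Written consequence in 6.2.1.3 |
|---|---|---|---|
| 1 | 0 | 1/6 | escalation permitted |
| 1 | 1 | 2/6 | no escalation |
| 0 | 2 | 2/6 | none stated for subjects 4–6 |
| 0 | 3 | 3/6 | none stated for subjects 4–6 |

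From 0/3, three more subjects can bring the total to at most 3/6.

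**Probability.** Assumptions, none of them given in the documents: independent subjects with a common true DLT rate p, exactly three initial subjects, and every 0/3 level filled to six. Let b(k) = C(3,k) p^k (1−p)^(3−k).

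- Given 0/3, chance of 2/6 or 3/6: G = b(2) + b(3)
- Unconditional chance of this path: b(0) × G
- Written condition met: W = b(0) + b(1) × b(0)
- Fewer than 2/6 counted over all six: F = b(0) × [b(0) + b(1)] + b(1) × b(0), which equals P(at most 1 DLT in 6)

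At p=1/3: b(0)=8/27, b(1)=12/27, b(2)=6/27, b(3)=1/27. So G = 7/27 = 25.9%, and the path has probability 8/27 × 7/27 = 56/729 = 7.7% (48/729 = 6.6% for 2/6 and 8/729 = 1.1% for 3/6). W = 312/729 = 42.8% and F = 256/729 = 35.1%. The difference W − F is again 56/729.

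| p | P(0/3) | G | Path | W | F |
|---|---|---|---|---|---|
| 0.10 | 72.9% | 2.8% | 2.0% | 90.6% | 88.6% |
| 0.20 | 51.2% | 10.4% | 5.3% | 70.9% | 65.5% |
| 0.25 | 42.2% | 15.6% | 6.6% | 60.0% | 53.4% |
| 0.30 | 34.3% | 21.6% | 7.4% | 49.4% | 42.0% |
| 1/3 | 29.6% | 25.9% | 7.7% | 42.8% | 35.1% |
| 0.40 | 21.6% | 35.2% | 7.6% | 30.9% | 23.3% |
| 0.50 | 12.5% | 50.0% | 6.3% | 17.2% | 10.9% |

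W describes only the written numeric condition. It gives no credit to the data reviews.

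**Other provisions that could fill the gap:**

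- *2–3/3 branch (6.2.1.3).* It fills the lower level to six and applies fewer than 2/6. It needs DLTs at a higher level, so it cannot act on Dose Level 3, the highest in the scheme.
- *Simultaneous escalation (6.2.1.4).* Any Arm 1 DLT at the current dose blocks this route, whichever subject has it. It does not govern independent escalation or expansion.
- *Pausing criteria (6.2.1.5).* They cover every subject but only part of the DLT list in 6.2.1.2. Grade 3 neurotoxicity, persistent Grade 3 CRS, Grade 4 organ toxicity and prolonged cytopenia, for example, are DLTs that are not themselves pausing criteria.
- *Replacement (4.1.1).* A cohort subject who misses Day 28 assessments is replaced. The section does not say that this must be settled before expansion opens.
- *Reviews (6.2.1.1, 6.2.2, Section 10).* They see all data and state no numeric limit.
- *Appendix 8.* The worked examples leave out accrual to six before expansion.

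**The case against.** A reader might infer that DLTs in subjects 4–6 enter no rule at all, and that a level with 2/6 or 3/6 is certain to clear. The documents do not support either reading. The 2–3/3 branch, 6.2.1.4 and the pausing criteria all use events in these subjects. A 0/3 result makes subjects eligible, but 6.2.1.1 still requires the Sponsor and treating investigators to review all DLT information from both arms before escalation is considered. Arm 1 expansion needs a dose to be identified as well as six enrolled, and the DMC reviews all clinical data before the Sponsor chooses that dose. The details are left to a DMC Charter that is not among the documents.

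Three further points have weight. The fewer-than-2/6 sentence can be read as a general definition of the MTD. Section 4.1.1, with the planned 36 evaluable subjects in 9.2, suggests that six evaluable per cohort was intended. The conditional figures can also mislead: 50% at p=0.50 applies only after a 0/3 result, which then occurs 12.5% of the time. In addition, filling a cohort to six is discretionary outside the Arm 1 requirement, and Appendix 8 shows Arm 1 levels with fewer than three subjects before escalation.

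These arguments narrow the point without removing it. None of the provisions states a limit for 0/3 followed by two or three DLTs, and a review without a limit does not explain why the same 2/6 stops escalation in one order and not in the other.

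**Conclusion.** The point holds in limited form. Once a level is 0/3, 2/6 or 3/6 reached through subjects 4–6 is not barred by a written numeric escalation or expansion limit, apart from the exceptions above. The gap is clearest at Dose Level 3. The Arm 1 trigger can also be met before those subjects complete the DLT window.

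Under the stated assumptions the path is uncommon overall, about 2% to 8% per level for p from 0.10 to 0.50. It matters most where the dose is too toxic and the first three subjects happen to have no DLT: given 0/3, the chance is 26% at p=1/3 and 50% at p=0.50.

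A reader might also infer that this trial's findings are compromised. They are not: SAP section 7 records that only two subjects received NTLA-5001 before termination, so no level reached a fourth subject. The value of the correction lies in the design text and any reuse of it.

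**What to change.** Reconcile the Synopsis, Protocol 4.1, 4.1.1, 6.2.1.3 and 6.2.2, and SAP 2.2, so that they answer two questions in the same way:

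1. Does the protocol's own limit of fewer than 2/6 count every DLT-evaluable subject treated at a level in that arm, however the subject was added?
2. Must the six Arm 1 subjects be DLT-evaluable, with Day 28 complete, before expansion opens, or is enrollment enough?

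The clinical rule is the sponsor's decision, and this point does not propose one.

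The cost is a short wording amendment with no added subjects or procedures. If the six must be evaluable, Arm 1 expansion may open up to about 28 days later. If the limit counts all six, a level would fail it more often, by the path probabilities tabulated above (2 percentage points at p=0.10, 8 at p=1/3).

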6.2.1.5 Criteria for Pausing or Stopping

If 1 of the criteria described below is reached, further enrollment of subjects will be suspended pending assessment by the Sponsor:

- any treatment-related death, or

- any Grade 4 CRS per ASTCT consensus criteria, that does not resolve to Grade 1 within 72 hours despite therapy, or
- any Grade 4 neurotoxicity per ASTCT ICANS consensus grading criteria for adults, that does not resolve to Grade 1 within 72 hours despite therapy, or
- evidence of any T cell proliferative disorder, or.
- any grade 3 or higher GVHD or Grade 2 GVHD that does not resolve to Grade 1 in response to systemic steroid therapy within 7 days.

If at the time enrollment is paused, and a subject has received lymphodepleting chemotherapy but has not yet received NTLA-5001, treatment with a lower dose of NTLA-5001 given to a prior cohort may be considered with agreement of the Sponsor and investigator.

An assessment of all available information will be completed by Sponsor in conjunction with the DMC. Resumption of enrollment and dosing will be decided by the Sponsor with recommendation from DMC.

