13.8 Appendix 8 Subject Accrual Order During Dose Escalation

Selected examples shown through dose selection in each Arm. Accrual of six subjects in cohorts prior to expansion is not shown. Each square represents 1 subject with dose level indicated by number. Symbol “*” indicates DLT. Symbol “•” indicates dose escalation decision.

1. No DLT observed

Arm 1	1	1	1	•	2	2	2	•	3	3	3			
Arm 2	1	1	1	•	2	2	2	•	3	3	3			

2. No DLT observed, Arm 1 accrual slower

Arm 1	1	1		•	2			•	3	3		3		
Arm 2	1	1	1	•	2	2	2	•	3	3	3			

3. Single DLT in Arm1, DL2

Arm 1	1	1	1	•	2	2	2*	2	2	2	•	3	3	3
Arm 2	1	1	1	•	2	2		2	•	3	3	3		

4. Single DLT in Arm1 DL2, Arm 1 accrual slower

Arm 1	1	1		•	2*	2	2	2	2	2	•	3		3	3
Arm 2	1	1	1	•	2	2	2	•	3	3	3				

5. Single DLT in Arm 2, DL2

Arm 1	1	1	1	•	2	2	2	•	3	3	3			
Arm 2	1	1	1	•	2	2*	2	2	2	2	•	3	3	3

6. MTD reached in Arm 1, DLT seen in 2/5 subjects at DL2†

Arm 1	1	1	1	•	2	2*	2	2	2*					
Arm 2	1	1	1	•	2		2	2						

7. MTD reached in Arm 2, DLT seen in 2/2 subjects at DL2

Arm 1	1	1	1	•	2	2	2	•	3	3	3			
Arm 2	1	1	1	•		2*	2*							

8. MTD reached in Arm 2, DLT seen in 2/3 subjects at DL2, Arm 1 accrual slower

Arm 1	1			•	2	2		2	•	3	3		3	
Arm 2	1	1	1	•	2*	2	2*							

† In Example #6 above, the MTD for subjects in Arm 1 is reached at a dose lower than the dose under evaluation in Arm 2. Accruing subjects in the order of Example #6 is not expected, because the risk of severe or serious adverse events after cell therapy is correlated with a subject’s tumor burden ([Garcia-Manero et al, 2015](#); [Garzon et al, 2017](#)). If, as in Example #6, the MTD for Arm 1 is reached at or below the dose under investigation in Arm 2, enrollment in Arm 2 will be paused and data reviewed by the Principal Investigators, Sponsor, and the DMC.

DL = dose level; DLT = dose-limiting toxicities; MTD = maximum tolerated dose

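### After one DLT in three, the dose-escalation text and Appendix 8 Example 6 give different stopping points for an expanded cohort with an early second DLT

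*Protocol*

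**What the plan says.** Four places in the protocol bear on this point.

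- **6.2.1.3, repeated in the synopsis (1.1).** If one of the initial group has a DLT, "enrollment will continue in the dose evaluation group for 3 additional subjects". The two possible outcomes of the expanded group are then listed under a single timing clause: "When the last subject in the expanded dose evaluation group has been observed through Day 28". The second outcome reads "If 1 or more additional subject in the expanded dose evaluation group experiences a DLT, no dose escalation will be proposed". The criterion for the level is "Fewer than 2/6 subjects with DLTs will establish the MTD".
- **6.2.1.1.** Within a cohort, "each of the first 3 subjects will be observed for 28 days before enrolling the next subject". No interval is stated between subjects 4, 5 and 6. The section refers the reader to the figure in 13.8 for the stagger.
- **13.8 (Appendix 8), Example 6.** The caption is "MTD reached in Arm 1, DLT seen in 2/5 subjects at DL2". The drawing shows one DLT among the first three subjects, a second in subject 5, and no sixth subject.
- **6.2.1.5.** Enrollment is suspended for a separate list of events, among them "any Grade 4 CRS per ASTCT consensus criteria, that does not resolve to Grade 1 within 72 hours despite therapy". A second DLT is not in itself on that list.

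**The concern.** Once a level has two DLTs, no later result can bring it under the 2-in-6 threshold, and escalation from it is already ruled out. Dosing the remaining added subjects at that level therefore cannot change the escalation decision. Yet 6.2.1.3 provides for three additional subjects and draws its conclusion only at the last one's Day 28, while the appendix cited for the stagger shows accrual ending at the second DLT.

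Two sites reading the same first-in-human protocol could stop at different points. Under one reading, up to two more subjects receive a dose that has already failed the protocol's own criterion. The missing stagger adds to this: if subjects 4 to 6 are dosed close together, the second DLT may be recognized too late to matter under either reading.

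**Working it through.** **The plan's own figures.** Escalation: 2 arms × 3 cohorts × 6 = 36. Total: 2 × (18 + 9) = 54. Both match the protocol. They are maxima that allow six subjects in every cohort, so they do not show which stopping point is meant.

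**Which failing results each reading can produce.** Start from exactly 1 DLT in the first three and require at least one more in subjects 4 to 6.

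| Reading | Possible failing results |
|---|---|
| 6.2.1.3 as worded (all three added subjects dosed) | 2/6, 3/6, 4/6 |
| Accrual ends at the second DLT | 2/4, 2/5, 2/6 |

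Example 6's 2/5 appears only in the second row.

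**How many could be dosed after the second DLT.** The documents give no DLT rate, so p is assumed to lie between 0.1 and 0.5. Outcomes are taken as independent and as known before the next subject is dosed.

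- If subject 4 has the second DLT (probability p), two subjects remain.
- If subject 5 has it (probability (1−p)p), one remains.
- If subject 6 has it, none remains.

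Given 1 DLT in 3:

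- Chance of at least one subject dosed after the second DLT: A = p + (1−p)p = 1 − (1−p)².
- Expected number so dosed: E = 2p + (1−p)p.

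The chance that a cohort starts with exactly 1 DLT in 3 is B = 3p(1−p)², so the chance per cohort is A × B.

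| p | A | E | B | A × B |
|---|---|---|---|---|
| 0.1 | 0.19 | 0.29 | 0.243 | 0.046 |
| 0.2 | 0.36 | 0.56 | 0.384 | 0.138 |
| 0.3 | 0.51 | 0.81 | 0.441 | 0.225 |
| 0.4 | 0.64 | 1.04 | 0.432 | 0.276 |
| 0.5 | 0.75 | 1.25 | 0.375 | 0.281 |

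For p = 0.3: A = 0.30 + 0.70 × 0.30 = 0.51; E = 0.60 + 0.21 = 0.81; B = 3 × 0.3 × 0.49 = 0.441; A × B = 0.225.

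If subjects 4 to 6 are dosed together, the table does not apply. Nobody is then dosed knowingly after a second DLT, but nobody can be spared either.

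**Whether the pausing criteria close the gap.** Setting the DLT definitions in 6.2.1.2 against 6.2.1.5:

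- DLTs that also pause enrollment: treatment-related death, Grade 4 CRS or ICANS that does not resolve to Grade 1 within 72 hours, and the listed GVHD.
- DLTs that do not: for example Grade 3 ICANS, Grade 4 CRS that does resolve to Grade 1 within 72 hours, and non-fatal Grade 4 organ toxicity.

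The backstop is therefore partial.

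**The case against.** The best defense is that 6.2.1.3 sets the time of the escalation decision and is silent on an early stop. Because 6.2.1.1 refers to the figure in 13.8, Example 6 can be read as filling that silence. There are other protections too: DMC consultation at any time, the sponsor's power to end enrollment at any time, SAE reporting within 24 hours, and immediate reporting of Grade 4 CRS and ICANS. And SAP section 7 records that only 2 subjects received NTLA-5001 before termination, so no expanded group was reached.

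Much of this stands. The text is silent; a reader might infer that it orders dosing to go on after a second DLT, but no sentence says so. A reader might also infer that no second DLT stops dosing; 6.2.1.5 shows that some do. Nor does Example 7 ("MTD reached in Arm 2, DLT seen in 2/2 subjects at DL2") add a second contradiction. It concerns the initial group, which 6.2.1.1 sets at up to three subjects and to which the last-subject Day 28 clause does not apply, so it is consistent with the text.

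What does not stand is that Example 6 merely completes the text. A provision for three additional subjects, judged after the last of them, does not fit a closure at five. A pausing event could halt a cohort at five, but the example mentions none at that level and gives the DLT count as its reason. The legend's remark that accrual to six before expansion is not drawn does not explain the missing subject: this level failed and was not heading for expansion, and Examples 3, 4 and 5 draw all six subjects after a single DLT. The footnote calling Example 6 unexpected concerns the order of the MTDs between arms, not the stop at five. The general protections are discretionary or concern reporting, and none fixes a stopping point.

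**Conclusion.** The inconsistency is real and confined to the expanded cohort: 6.2.1.3 and its synopsis copy against Appendix 8 Example 6, with 6.2.1.1 leaving the stagger for subjects 4 to 6 unstated. As worded, the text permits dosing at a level that can no longer meet its own criterion.

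At most two subjects per expanded cohort are affected. The conditional chance that at least one is dosed after the second DLT runs from 19% at p = 0.1 to 75% at p = 0.5; per cohort it is about 5%, 14%, 22%, 28% and 28% across the five assumed rates. These figures rest on an assumed DLT rate, independence, and outcomes known in turn. The conditional figures should not be read as the risk in every cohort.

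The gap had no effect on the subjects treated here and no SAP analysis depends on it. It remains a contradiction in a safety rule that should be corrected, particularly if the wording is reused.

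**What to change.** Reconcile the synopsis, 6.2.1.1 and 6.2.1.3 with Appendix 8 Example 6, so that all of them give one stopping point for an expanded cohort after a second DLT. State in 6.2.1.1 whether the 28-day stagger applies to subjects 4 to 6. Which stopping point and which stagger are right is for the sponsor and the DMC to decide.

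The cost is one or two sentences in 6.2.1.1 and 6.2.1.3, the matching synopsis edit and, depending on the choice, a redrawn Example 6. If the stagger is stated to continue, accrual may slow, but only in cohorts with 1 DLT in the first 3.

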------------------------------	---

	
disorder (per CTCAE); Grade 3 cardiac, respiratory, or vascular disorder that does not resolve to Grade 2 or lower within 72 hours; or Grade 3 hepatobiliary or renal disorder that does not resolve to Grade 2 or lower within 7 days.
 
• Grade 5 events without clinical or radiological evidence of disease progression which are related to NTLA 5001. 
Dose Escalation and Dose Reduction Decisions
 
If none of the initial dose evaluation group subjects experience a DLT, subjects in the treatment phase who have not yet received NTLA-5001 and subsequent subjects entering the treatment phase will be eligible for the next dose escalation cohort.
 
If 1 of the initial dose evaluation group subjects experiences a DLT, enrollment will continue in the dose evaluation group for 3 additional subjects. When the last subject in the expanded dose evaluation group has been observed through Day 28:
 
• If no subject in the expanded dose evaluation group experiences a DLT, subjects in the treatment phase who have not yet received NTLA-5001 and subsequent subjects entering the treatment phase will be eligible for the next dose escalation cohort.• If 1 or more additional subject in the expanded dose evaluation group experiences a DLT, no dose escalation will be proposed. Subjects in the treatment phase who have not yet received NTLA-5001 and subsequent subjects entering the treatment phase will be eligible for Dose Level -1 if DLTs are seen at Dose Level 1, or the next lower dose level will be declared the maximum tolerated dose (MTD), if DLTs are seen at Dose Level 2 or 3. Fewer than 2/6 subjects with DLTs will establish the MTD. 
If 2 or 3 of the initial dose evaluation group experiences a DLT, no dose escalation will be proposed. Subjects in the treatment phase who have not yet received NTLA-5001 and subsequent subjects entering the treatment phase will be eligible for Dose Level -1 if DLTs are seen at Dose Level 1, or the next lower dose level will be expanded to 6 subjects if DLTs are seen at Dose Level 2 or 3. Fewer than 2/6 subjects with DLTs will establish the MTD.
 
If a dose escalation is proposed, the subsequent cohort dose may be reduced or increased by up to 50% if the Sponsor and investigator agree, based on observations in the prior cohort. At the Sponsor's discretion, up to 6 subjects may be enrolled in any dose cohort for Arm 1 or Arm 2.
 
Simultaneous Escalation of Arm 1 and Arm 2
 
The risk of severe or serious adverse events after cell therapy is correlated with a subject's tumor burden (Garcia-Manero et al, 2015; Garzon et al, 2017). Therefore, DLT information from Arm 2 subjects with $\geq 5\%$ bone marrow blasts may inform dose escalation decisions for Arm 1 subjects with $< 5\%$ bone marrow blasts. Simultaneous escalation of Arm 1 and Arm 2 may occur when the following criteria are met:
 
1. Dose escalation in Arm 2 is recommended from the current dose based on Dose Escalation and Dose Reduction criteria above; and2. No subjects have experienced DLT at the current dose in Arm 1.

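### One failure branch of the escalation rule declares the next lower dose the MTD without requiring the 6 subjects that the plan's own fewer-than-2/6 standard needs

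*Protocol*

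**What the plan says.** Under Protocol 6.2.1.3 an initial group of up to 3 subjects is treated at each level. With no DLT the Arm escalates. With 1 DLT, 3 more subjects are added, and the Arm escalates if none of those has a DLT. There are two ways to fail at Dose Level 2 or 3:

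- **First branch** (1 DLT in the first 3, then at least one more): "or the next lower dose level will be declared the maximum tolerated dose (MTD), if DLTs are seen at Dose Level 2 or 3".
- **Second branch** (2 or 3 DLTs in the first 3): "or the next lower dose level will be expanded to 6 subjects if DLTs are seen at Dose Level 2 or 3".

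Each branch ends with the same sentence: "Fewer than 2/6 subjects with DLTs will establish the MTD". The synopsis repeats the first-branch wording: "the next lower dose level will be declared the maximum tolerated dose (MTD), if DLTs are seen at Dose Level 2 or 3". A later sentence in 6.2.1.3 leaves further enrolment to the sponsor's discretion: "up to 6 subjects may be enrolled in any dose cohort for Arm 1 or Arm 2".

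Section 6.2.1.4 lets Arm 1 move up together with Arm 2 when Arm 2 qualifies to escalate and "No subjects have experienced DLT at the current dose in Arm 1". It sets no minimum number of Arm 1 subjects. Appendix 8 Example 2, titled "No DLT observed, Arm 1 accrual slower", shows Arm 1 leaving Dose Level 1 after 2 subjects and Dose Level 2 after 1.

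**The concern.** The two branches differ only in how the higher level failed. The evidence on the lower level can be identical, yet one branch orders it completed to 6 and the other declares it the MTD. The documents give no reason for the difference. A level passed on 0/3 cannot show fewer than 2 DLTs among 6 subjects, and nor can an Arm 1 level passed on 1 or 2 subjects.

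At stake is whether a declared MTD has met the plan's own evidential standard, and whether two sites or two reviewers reading the rule would act alike.

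**Working it through.** **The plan's own figures.** 3 levels x 6 subjects x 2 Arms = 36 in escalation. Adding 2 x 9 in expansion gives 54. Both agree with the synopsis and Protocol 9.2, so six subjects at every level are already budgeted.

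**Does Appendix 8 settle the reading?** Example 6 ("MTD reached in Arm 1, DLT seen in 2/5 subjects at DL2") is a first-branch failure. Examples 7 and 8 are second-branch failures. All three are labelled as having reached the MTD, with three subjects drawn at Dose Level 1 in the affected Arm. The caption says that accrual to six before expansion is not drawn, and says nothing about six before an MTD is declared. So the figure shows a fill-up in neither branch and does not decide the matter.

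**How often it bites.** The documents give no DLT rates, so the curves below are assumptions. The calculation is exact for one Arm, with 3 then 3 subjects per level, no simultaneous escalation and no discretionary enrolment. For true DLT rate p and q = 1 - p at a level:

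- passed on 0/3: E0 = q³
- passed on 1/6: E1 = 3pq² x q³
- first-branch failure: A = 3pq² x (1 - q³)
- second-branch failure: B = 3p²q + p³
- pass = E0 + E1

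MTD declared directly on 3 subjects: D = E0(1)A(2) + pass(1)E0(2)A(3).

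Same branch, lower level already at 1/6: D6 = E1(1)A(2) + pass(1)E1(2)A(3).

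Filling changes the declared level when 2 or more of the next 3 subjects have a DLT, which has probability B at the lower level: C = E0(1)A(2)B(1) + pass(1)E0(2)A(3)B(2).

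If a filled Dose Level 2 fails and Dose Level 1 stands at 0/3, a second fill-up follows: S = E0(1)E0(2)A(3)B(2). Expected extra subjects = 3(D + S).

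Worked for 10/20/40%:

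- Dose Level 1: E0 = 0.729, E1 = 0.1771, pass = 0.9061, B = 0.028.
- Dose Level 2: E0 = 0.512, A = 0.1874, B = 0.104.
- Dose Level 3: A = 0.3387.
- D = 0.729 x 0.1874 + 0.9061 x 0.512 x 0.3387 = 0.1366 + 0.1571 = 0.2937.
- C = 0.1366 x 0.028 + 0.1571 x 0.104 = 0.0202.
- S = 0.729 x 0.512 x 0.3387 x 0.104 = 0.0131.
- Extra subjects = 3 x (0.2937 + 0.0131) = 0.92.

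| Assumed DLT rates, levels 1/2/3 | Declared on 3 (D) | First-branch stops already at 6, D6/(D+D6) | Level changed by filling (C) | Expected extra subjects |
|---|---|---|---|---|
| 10/20/40% | 29.4% | 24% | 2.0% | 0.92 |
| 20/35/50% | 22.9% | 29% | 3.5% | 0.72 |
| 25/40/55% | 18.2% | 30% | 3.6% | 0.58 |
| 15/30/45% | 27.3% | 27% | 3.1% | 0.87 |
| 5/10/20% | 18.9% | 17% | 0.4% | 0.58 |

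D and C are shares of all single-arm escalations. If the sponsor used its discretion to fill half of the 3-subject cases, independently of the data, D would fall to between 9.1% and 14.7% and C to between 0.2% and 1.8%.

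**The case against.** The strongest reply is that the condition is already in the branch. The fewer-than-2/6 sentence directly follows the declaration, 0/3 does not satisfy it, and the sponsor may enrol up to 6 in any cohort. On that reading only a reminder to enrol is missing. The reading is possible and may well be what was meant. It does not remove the conflict, because the same closing sentence follows the second branch, where the authors still thought it necessary to order the missing subjects. In the first branch they wrote a declaration and left enrolment to discretion.

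It is also fair to say that little hangs on the MTD label. The escalation objective is to identify a dose for expansion. Under 6.2.2 the DMC recommends a dose or range and the sponsor decides. Protocol 4.1 requires 6 Arm 1 subjects at the dose before Arm 1 expansion. The footnote to Example 6 pauses Arm 2 for review if the Arm 1 MTD is reached at or below the dose under study in Arm 2. All of this stands and keeps the point small.

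Two stronger readings should be resisted:

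- A reader might infer that Arm 2 wrongly lacks the 6-subject gate before expansion. The documents do not show an error there. Arm 2 cohorts hold 3 to 6 subjects, whereas only Arm 1 can advance on the other Arm's data with fewer than 3, so a gate for Arm 1 alone fits that asymmetry. Adding one for Arm 2 would be a new design requirement.
- A reader might take the simultaneous-escalation case as the headline. From 0/1, completing to 6 finds 2 or more DLTs with probability 1 - q⁵ - 5pq⁴ = 8.1%, 26.3% and 57.2% at true rates of 10%, 20% and 35%. Those figures are conditional on Arm 2 having passed that dose and on a later first-branch failure in Arm 1. At 35% in both Arms, Arm 2 passes with probability 0.40, and Arm 2 passing together with 0/1 in Arm 1 has probability 0.40 x 0.65 = 0.26. The 57.2% is not a rate at which the trial would go wrong.

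**Conclusion.** The first branch is wrong as written, and the point is minor. It permits an MTD declaration that does not meet the standard stated in the same paragraph whenever the lower level was passed with fewer than 6 subjects. Where that level already stands at 1/6 the branches agree.

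On the assumed curves the literal rule is used often (18% to 29% of single-arm escalations), but completing the level would seldom alter the outcome (0.4% to 3.6%). These sizes rest on assumed DLT rates and no discretionary filling.

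A reader might infer that an untested dose would go straight into expansion, or that the trial's findings are compromised. The documents support neither: expansion dose selection is a separate decision, and SAP Section 7 records that only 2 subjects had received NTLA-5001 when the sponsor terminated the study. The value of the correction lies in clear wording and in any reuse of this escalation rule.

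**What to change.** In the first branch of 6.2.1.3 and its synopsis copy, replace the declaration with the second branch's instruction: the next lower level is expanded to 6 subjects, if fewer than 6 have been treated. Keep fewer than 2/6 as the MTD condition in both branches and both Arms, including Arm 1 levels passed by simultaneous escalation. Add that if 2 or more of 6 have DLTs at the filled level, the same rule applies to the next lower level, with Dose Level -1 below Dose Level 1. Leave the Appendix 8 example labels alone, and extend the caption to say that accrual to six before the MTD is established is also not shown in Examples 6 to 8.

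The cost is up to 3 more subjects at a level passed on 3 (4 or 5 where Arm 1 passed it on 2 or 1) and at least one further 28-day observation period. The expected addition is about 0.58 to 0.92 subjects per single-arm escalation, counting first-branch fill-ups at Dose Levels 1 and 2 and a second fill-up where needed, but not subjects later treated at Dose Level -1. Fill-ups at Dose Levels 1 to 3 stay within 6 per cohort, 36 in escalation and 54 in total. Only if Dose Levels 3, 2 and 1 all failed in turn would Dose Level -1 add a fourth cohort to an Arm. By the first-branch route that has probability S x B(1), at most about 0.15% on these curves (0.0097 x 0.156 for 25/40/55%).
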